### **8.7. Hospitalization**

Hospitalization is defined as any initial admission (even less than 24 hours) in a hospital or equivalent healthcare facility or any prolongation of an existing admission. Admission also includes transfer within the hospital to an acute/intensive care unit (eg, from the psychiatric wing to a medical floor, medical floor to a coronary care unit, or neurological floor to a tuberculosis unit). An emergency room visit does not necessarily constitute an hospitalization; however, the event leading to the emergency room visit should be assessed for medical importance.

Hospitalization does not include the following:

- Rehabilitation facilities;
- Hospice facilities;
- Respite care (eg, caregiver relief);
- Skilled nursing facilities;
- Nursing homes;
- Same-day surgeries (as outpatient/same day/ambulatory procedures).

Hospitalization or prolongation of hospitalization in the absence of a precipitating, clinical AE is not in itself an SAE. Examples include:

- Admission for treatment of a preexisting condition not associated with the development of a new AE or with a worsening of the preexisting condition (eg, for workup of persistent pre-treatment laboratory abnormality);
- Social admission (eg, patient has no place to sleep);
- Administrative admission (eg, for yearly physical examination);
- Protocol-specified admission during a study (eg, for a procedure required by the study protocol);
- Optional admission not associated with a precipitating clinical AE (eg, for elective cosmetic surgery);
- Hospitalization for observation without a medical AE;
- Preplanned treatments or surgical procedures. These should be noted in the baseline documentation for the entire protocol and/or for the individual patient;
- Admission exclusively for the administration of blood products.

Diagnostic and therapeutic noninvasive and invasive procedures, such as surgery, should not be reported as AEs. However, the medical condition for which the procedure was performed should be reported if it meets the definition of an AE. For example, an acute appendicitis that begins during the AE reporting period should be reported as the AE, and the resulting appendectomy should be recorded as treatment of the AE.

### 8.8. Severity Assessment

| GRADE | Clinical Description of Severity   |
|-------|--|
| 0     | No Change from normal or reference range (This grade is not included in the Version 4.03 CTCAE document but may be used in certain circumstances.) |
| 1     | MILD adverse event   |
| 2     | MODERATE adverse event   |
| 3     | SEVERE adverse event   |
| 4     | LIFE-THREATENING consequences; urgent intervention indicated   |
| 5     | DEATH RELATED TO adverse event   |

Note the distinction between the severity and the seriousness of an AE. A severe event is not necessarily an SAE. For example headache may be severe (interferes significantly with the patient's usual function) but would not be classified as serious unless it met one of the criteria for SAEs listed above.

## 8.9. Causality Assessment

The investigator's assessment of causality must be provided for all AEs (serious and non-serious); the investigator must record the causal relationship in the CRF, as appropriate, and report such an assessment in accordance with the SAE reporting requirements if applicable. An investigator's causality assessment is the determination of whether there exists a reasonable possibility that the investigational product caused or contributed to an AE; generally the facts (evidence) or arguments to suggest a causal relationship should be provided. If the investigator does not know whether or not the investigational product caused the event, then the event will be handled as "related to investigational product" for reporting purposes, as defined by the sponsor (see the section on [Reporting Requirements](#)). If the investigator's causality assessment is "unknown but not related to investigational product," this should be clearly documented on study records.

In addition, if the investigator determines that an SAE is associated with study procedures, the investigator must record this causal relationship in the source documents and CRF, as appropriate, and report such an assessment in accordance with the SAE reporting requirements, if applicable.

## 8.10. Exposure During Pregnancy

For both unapproved/unlicensed products and for marketed products, an exposure during pregnancy occurs if:

1. A female becomes, or is found to be, pregnant either while receiving or having been exposed (eg, because of treatment or environmental exposure) to the investigational product; or the female becomes or is found to be pregnant after discontinuing and/or being exposed to the investigational product;

An example of environmental exposure would be a case involving direct contact with a Pfizer product in a pregnant women (eg, a nurse reports that she is pregnant and has been exposed to chemotherapeutic products).

2. A male has been exposed (eg, because of treatment or environmental exposure) to the investigational product prior to or around the time of conception and/or is exposed during his partner's pregnancy.

If a study patient or study patient's partner becomes or is found to be pregnant during the study patient's treatment with the investigational product, the investigator must submit this information to the Pfizer drug safety unit on an SAE report form and an EDP supplemental form, regardless of whether an SAE has occurred. In addition, the investigator must submit information regarding environmental exposure to a Pfizer product in a pregnant woman (eg, a patient reports that she is pregnant and has been exposed to a cytotoxic product by inhalation or spillage) using the EDP supplemental form. This must be done irrespective of whether an AE has occurred and within 24 hours of awareness of the exposure. The information submitted should include the anticipated date of delivery (see below for information related to termination of pregnancy).

Follow-up is conducted to obtain general information on the pregnancy and its outcome for all EDP reports with an unknown outcome. The investigator will follow the pregnancy until completion (or until pregnancy termination) and notify Pfizer of the outcome as a follow-up to the initial EDP supplemental form. In the case of a live birth, the structural integrity of the neonate can be assessed at the time of birth. In the event of a termination, the reason(s) for the termination should be specified and, if clinically possible, the structural integrity of the terminated fetus should be assessed by gross visual inspection (unless preprocedure test findings are conclusive for a congenital anomaly and the findings are reported).

If the outcome of the pregnancy meets the criteria for an SAE (ie, ectopic pregnancy, spontaneous abortion, intrauterine fetal demise, neonatal death, or congenital anomaly [in a live-born baby, a terminated fetus, an intrauterine fetal demise or a neonatal death]), the investigator should follow the procedures for reporting SAEs.

Additional information about pregnancy outcomes that are reported as SAEs follows:

- Spontaneous abortion includes miscarriage and missed abortion;
- Neonatal deaths that occur within 1 month of birth should be reported, without regard to causality, as SAEs. In addition, infant deaths after 1 month should be reported as SAEs when the investigator assesses the infant death as related or possibly related to exposure to the investigational product.

Additional information regarding the EDP may be requested by the investigator. Further follow-up of birth outcomes will be handled on a case-by-case basis (eg, follow-up on preterm infants to identify developmental delays). In the case of paternal exposure, the investigator will provide the study patient with the Pregnant Partner Release of Information Form to deliver to his partner. The investigator must document in the source documents that the patient was given the Pregnant Partner Release of Information Form to provide to his partner.

### **8.11. Occupational Exposure**

An occupational exposure occurs when, during the performance of job duties, a person (whether a healthcare professional or otherwise) gets in unplanned direct contact with the product, which may or may not lead to the occurrence of an AE.

An occupational exposure is reported to the drug safety unit within 24 hours of the investigator's awareness, using the SAE report form, regardless of whether there is an associated AE/SAE. Since the information does not pertain to a patient enrolled in the study, the information is not reported on a CRF; however, a copy of the completed SAE report form is maintained in the investigator site file.

### **8.12. Withdrawal Due to Adverse Events (See also the Section on [Patient Withdrawal](#))**

Withdrawal due to AEs should be distinguished from withdrawal due to other causes, according to the definition of AE noted earlier, and recorded on the appropriate AE CRF page.

When a patient withdraws because of an SAE, the SAE must be reported in accordance with the reporting requirements defined below.

### **8.13. Eliciting Adverse Event Information**

The investigator is to report all directly observed AEs and all AEs spontaneously reported by the study patient. In addition, each study patient will be questioned about AEs.

### **8.14. Reporting Requirements**

Each AE is to be assessed to determine if it meets the criteria for SAEs. If an SAE occurs, expedited reporting will follow local and international regulations, as appropriate.

#### **8.14.1. Serious Adverse Event Reporting Requirements**

If an SAE occurs, Pfizer is to be notified within 24 hours of investigator awareness of the event. In particular, if the SAE is fatal or life-threatening, notification to Pfizer must be made immediately, irrespective of the extent of available AE information. This time frame also applies to additional new information (follow-up) on previously forwarded SAE reports as well as to the initial and follow-up reporting of EDP, exposure via breastfeeding, and occupational exposure cases.

In the rare event that the investigator does not become aware of the occurrence of an SAE immediately (eg, if an outpatient study patient initially seeks treatment elsewhere), the investigator is to report the event within 24 hours after learning of it and document the time of his or her first awareness of the AE.

For all SAEs, the investigator is obligated to pursue and provide information to Pfizer in accordance with the time frames for reporting specified above. In addition, an investigator may be requested by Pfizer to obtain specific additional follow-up information in an expedited fashion. This information collected for SAEs is more detailed than that captured on the AE CRF. In general, this will include a description of the AE in sufficient detail to allow for a complete medical assessment of the case and independent determination of possible causality. Information on other possible causes of the event, such as concomitant medications, vaccines, and/or illnesses, must be provided. In the case of a patient death, a summary of available autopsy findings must be submitted as soon as possible to Pfizer or its designated representative.

#### **8.14.2. Non-Serious Adverse Event Reporting Requirements**

All AEs will be reported on the AE page(s) of the CRF. It should be noted that the form for collection of SAE information is not the same as the AE CRF. Where the same data are collected, the forms must be completed in a consistent manner. For example, the same AE term should be used on both forms. AEs should be reported using concise medical terminology on the CRFs as well as on the form for collection of SAE information.

### **8.14.3. Sponsor's Reporting Requirements to Regulatory Authorities**

AE reporting, including suspected unexpected serious adverse reactions, will be carried out in accordance with applicable local regulations.

## **9. DATA ANALYSIS/STATISTICAL METHODS**

Detailed methodology for summary and statistical analyses of the data collected in this study will be documented in a statistical analysis plan (SAP), which will be maintained by the sponsor. This document may modify the plans outlined in the protocol; however, any major modifications of the primary endpoint definition and/or its analysis will also be reflected in a protocol amendment.

### **9.1. Analysis Sets**

#### 1. Safety analysis set.

The safety analysis set includes all enrolled patients who receive at least one dose of study treatment.

#### 2. Full analysis set.

The full analysis set includes all enrolled patients.

#### 3. Per-protocol analysis set (evaluable for MTD).

The per-protocol analysis set includes all enrolled patients who receive at least one dose of study treatment and who do not have major treatment deviations during the 28-day observation period. Patients with major treatment deviations in this cycle are not evaluable for the MTD assessment and will be replaced as needed to permit MTD estimation. Major treatment deviations include:

- Administration of less than 50% of the planned dose of PF-06840003, provided that it is not due to toxicity attributable to PF-06840003
- Administration of more than 150% of the planned dose of PF-06840003

#### 4. PK analysis sets

The PK parameter analysis population is defined as all enrolled patients treated who have sufficient information to estimate at least 1 of the PK parameters of interest.

The PK concentration population is defined as all enrolled patients who are treated and have at least 1 analyte concentration.

#### 5. Biomarker analysis set(s)

The biomarker analysis set includes all enrolled patients with at least one of the PD/biomarker parameters evaluated at pre- and/or post-dose.

## **9.2. Statistical Methods and Properties**

### **9.2.1. Statistical Methods for Dose Escalation/De-Escalation**

Part 1, the dose escalation phase of this study, employs an mTPI design to estimate the MTD. The mTPI design employs a simple beta binomial model with a conjugated prior beta (0.5, 0.5). Decision rules are based on calculating the unit probability mass (UPM) of 3 intervals corresponding to underdosing, proper dosing, and overdosing in terms of dose limiting toxicity. A proper dosing interval is centered at the target toxicity rate (pT) of 27.5% with 5% uncertainty ( $0.225 < pT < 0.325$ ). The under dosing interval is (0, 0.225), and the overdosing interval is (0.325, 1). The 3 dosing intervals are associated with 3 different dose escalation decisions. The underdosing interval corresponds to a dose escalation I, overdosing corresponds to a dose de-escalation, and proper dosing corresponds to staying at the same current dose. Given an interval and a probability distribution, the UPM of that interval is defined as the probability of the interval divided by the length of the interval. The mTPI design calculates the UPMs for the 3 dosing intervals, and the one with the largest UPM implies the corresponding dose finding decision. That decision provides the dose level to be used for future patients. For example, if the underdosing interval has the largest UPM, decision E (to escalate) will be executed, and the next cohort of patients will be treated at the next higher dose level. Under the mTPI design, a trial is terminated when either the lowest dose is above the MTD or a pre-specified maximum sample size is reached. Doses with an incidence of DLT >33% (eg, 4 out of 10) will not be declared as MTD even though it is allowed by the mTPI method.

### **9.3. Sample Size Determination**

Due to the dynamic nature of the Bayesian allocation procedure, the sample size using the mTPI approach cannot be determined in advance in the dose escalation phase of the study. The target sample size for each cohort is 2 to 4, the actual number of patients treated at each dose will vary from 2 to 12. It is estimated no more than approximately 72 DLT evaluable patients will be enrolled in the dose escalation stage in order to have a reliable and accurate estimate of the MTD, although this may be higher if more than 6 dose levels are required to be evaluated. Up to approximately 20 to 25 patients are anticipated to be enrolled in Part 2 of the study.

In Part 2, the expansion phase of the study, multiple efficacy endpoints will be investigated, namely: 1) disease control rate (DCR) at Week 9; 2) DCR at Week 25; 3) objective response rate (ORR) by MRI by or at Week 9; 4) ORR by F-18-FLT-PET scan by or at Week 9 (if collected). The sample size is driven by DCR at Week 9 and ORR by MRI.

The expansion phase of the study will be a single arm study, the recommended dose from Part 1 will be used in this phase. With 20 patients, the study will have an approximately 75% power to detect a 25% improvement in Disease Control Rate (DCR), aiming for a 65% DCR, from the null hypothesis of 40% DCR. The study will have an approximately 78% power to detect a 15% improvement in ORR, aiming for a 20% ORR, from the null hypothesis of 5% ORR. These sample size calculations use an one-sample test for a single proportion with an one-sided alpha level of 0.05. The statistical power will be slightly higher than stated above if this phase of the study enrolls more than 20-25 patients.

As data accumulates, a Bayesian approach with a non-informative Jeffery's prior beta (0.5,0.5) will be used to calculate the posterior probability of observing certain DCR and ORR. For example, if 2 responders were observed in the first 10 patients enrolled, the posterior probability of observing 20% ORR is about 53.3%; if 2 responders were observed in the first 12 patients enrolled, the posterior probability of observing 20% ORR is about 41.5%; if only 1 responder was observed in the first 15 patients enrolled, the posterior probability of observing 20% ORR is about 8.7%. If a posterior probability is less than 15% for both of the 2 efficacy endpoints, the study team may choose to stop the expansion phase for futility. The safety data will also be reviewed in that decision-making process.

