#### **9.4. Efficacy Analysis**

There is no efficacy analysis in the dose escalation phase of the study (Part 1).

In the expansion phase (Part 2), anti-tumor activity is one of the two primary objectives.

Tumor assessment in the study will be based on the Macdonald criteria. DCR, ORR, duration of response (DOR), and Progression-Free Survival (PFS) will be calculated and presented. For binary variable (eg, ORR, DCR), descriptive statistics will be used; for time-to-event variables (eg, DOR, PFS), Kaplan-Meier analysis may be performed. The detailed analyses will be described in the statistical analysis plan.

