4.3. Sample Size Determination

Due to the dynamic nature of the Bayesian allocation procedure, the sample size using the mTPI approach cannot be determined in advance in the dose escalation phase of the study. The target sample size for each cohort is 2 to 4, the actual number of patients treated at each dose will vary from 2 to 12. It is estimated that the maximum sample size will be approximately 72 patients in Part 1 of the study, although this may be higher if more than 6 dose levels are required to be evaluated. Up to approximately 20 to 25 patients are anticipated to be enrolled in Part 2 of the study.

In Part 2, the expansion phase of the study, multiple efficacy endpoints will be investigated, namely: 1) disease control rate (DCR) at Week 9; 2) DCR at Week 25; 3) objective response rate (ORR) by MRI by or at Week 9; 4) ORR by F-18-FLT-PET scan by or at Week 9 (if collected). The sample size is driven by DCR at Week 9 and ORR by MRI.

The expansion phase of the study will be a single arm study, the recommended dose from Part 1 will be used in this phase. With 20 patients, the study will have an approximately 75% power to detect a 25% improvement in Disease Control Rate (DCR), aiming for a 65% DCR, from the null hypothesis of 40% DCR. The study will have an approximately 78% power to detect a 15% improvement in ORR, aiming for a 20% ORR, from the null hypothesis of 5% ORR. These sample size calculations use a one-sample test for a single

proportion with a one-sided alpha level of 0.05. The statistical power will be slightly higher than stated above if this phase of the study enrolls more than 20-25 patients.

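### At 20 patients, no responder cut-off gives both the Part 2 power the plan states and its one-sided alpha of 0.05, most clearly for ORR

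*Protocol*

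**What the plan says.** Protocol 9.3 gives the planned size of the expansion phase ("Up to approximately 20 to 25 patients are anticipated to be enrolled in Part 2 of the study") and its basis: "The sample size is driven by DCR at Week 9 and ORR by MRI". For DCR it states "With 20 patients, the study will have an approximately 75% power to detect a 25% improvement in Disease Control Rate (DCR", and SAP 4.3 repeats the same rates, "aiming for a 65% DCR, from the null hypothesis of 40% DCR". For ORR it states "approximately 78% power to detect a 15% improvement in ORR, aiming for a 20% ORR, from the null hypothesis of 5% ORR". The only description of the method is "These sample size calculations use an one-sample test for a single proportion with an one-sided alpha level of 0.05". Neither document says whether that test is exact or approximate, and neither gives a responder cut-off. Both add: "The statistical power will be slightly higher than stated above if this phase of the study enrolls more than 20-25 patients".

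On analysis, Protocol 9.4 says "For binary variable (eg, ORR, DCR), descriptive statistics will be used". SAP 4.1 says the study has no statistical hypotheses, although SAP 4.3 sizes Part 2 against null values of 40% and 5%.

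**The concern.** With 20 patients and a binary endpoint, few cut-offs are relevant, and each has its own fixed false-positive rate and power. A normal approximation treats the count as continuous, so it can report a power and an alpha that no single cut-off has. The risk is greatest for ORR, where the expected number of responders under the null is only 20 × 0.05 = 1.

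DCR at Week 9 and ORR by MRI are the endpoints said to drive the size, and evaluating efficacy is a primary objective of Part 2. From the text, a reader would infer a 25% (DCR) or 22% (ORR) chance of missing the target effect at a 5% false-positive rate. If the design cannot have those properties, the justification for 20 patients is misdescribed, and a result near a cut-off would be read against the wrong error rates.

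**Working it through.** **Inputs (Protocol 9.3, SAP 4.3).** n = 20, planned range 20 to 25. DCR: p0 = 0.40, p1 = 0.65. ORR: p0 = 0.05, p1 = 0.20. One-sided alpha 0.05, z = 1.645.

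**Step 1: reproduce the stated figures.** Uncorrected score z-test, with the null variance for the critical value and the alternative variance for power:

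power = Φ{[p1 − p0 − 1.645·√(p0(1−p0)/n)] / √(p1(1−p1)/n)}

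- DCR: (0.25 − 1.645 × 0.1095) / 0.1067 = 0.655, so power = 74.4% (stated: about 75%).
- ORR: (0.15 − 1.645 × 0.0487) / 0.0894 = 0.781, so power = 78.3% (stated: about 78%).

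Other common one-sided approximations at n = 20 fail on at least one endpoint (DCR / ORR): Wald with alternative variance 75.8% / 51.3%; null variance only 73.8% / 92.4%; arcsine 73.2% / 68.6%; continuity-corrected score 66.3% / 69.2%. That the uncorrected score form was used is therefore an inference, but a well-supported one.

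**Step 2: exact binomial properties at n = 20.** True alpha = P(X ≥ r | p0); power = P(X ≥ r | p1).

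| Endpoint | Cut-off | True alpha | Power |
|---|---|---|---|
| DCR | ≥11 | 0.1275 | 87.8% |
| DCR | ≥12 | 0.0565 | 76.2% |
| DCR | ≥13 | 0.0210 | 60.1% |
| ORR | ≥2 | 0.2642 | 93.1% |
| ORR | ≥3 | 0.0755 | 79.4% |
| ORR | ≥4 | 0.0159 | 58.9% |

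The z-test rejects above n·p0 + 1.645·√(n·p0(1−p0)). That is 11.60 for DCR (so ≥12) and 2.60 for ORR (so ≥3). These are the only cut-offs near the stated powers, and both exceed 0.05: DCR by 0.0065 (13% relative), ORR by 0.0255 (51% relative).

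**Step 3: across the planned range.** Power, with true alpha in brackets for the z-test cut-offs:

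| n | DCR, exact test at 0.05 | DCR, z-test cut-off | ORR, exact test at 0.05 | ORR, z-test cut-off |
|---|---|---|---|---|
| 20 | 60.1% | 76.2% (0.057) | 58.9% | 79.4% (0.076) |
| 21 | 70.6% | 70.6% (0.035) | 63.0% | 82.1% (0.085) |
| 22 | 64.7% | 79.2% (0.055) | 66.8% | 84.6% (0.095) |
| 23 | 74.1% | 74.1% (0.035) | 70.3% | 86.7% (0.105) |
| 24 | 68.7% | 81.7% (0.054) | 73.6% | 88.6% (0.116) |
| 25 | 77.1% | 77.1% (0.034) | 76.6% | 76.6% (0.034) |

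At n = 25 the z-test limits are 14.03 and 3.04, so both methods use ≥15 for DCR and ≥4 for ORR, and power and alpha agree.

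**Step 4: the sentence on higher power with more patients.** Exact power at every n from 21 to 40 is above exact power at n = 20; the minima are 64.7% (DCR, n = 22) and 63.0% (ORR, n = 21). The general direction is right. But the sentence promises more than the stated 75% and 78% above 25 patients, and the exact test at 0.05 does not always give that: DCR power is 72.2% at n = 26 and ORR power is 71.6% at n = 29.

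**The case against.** The strongest reply is that nothing in the trial turns on these alphas. DCR and ORR are summarised descriptively, the SAP disclaims hypotheses and any formal interim analysis, and the only efficacy-based decision is an optional futility look that uses posterior probabilities. The plan also says approximately, and a standard formula does return its figures. The DCR excess is small, and the material one concerns ORR, a secondary endpoint. A mid-p criterion would accept both cut-offs (0.0388 for DCR ≥12, 0.0457 for ORR ≥3). On the approximation's own formula, power rises steadily, to 82.4% and 83.6% at n = 25.

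Much of this stands as a limit on the consequences: no false-positive claim can arise from a test that is not planned, and the stated powers are not miscalculated. It does not rescue the statement itself. The word approximately qualifies the power, not the alpha, and does not stretch to 58.9% against 78% or to 0.0755 against 0.05. Mid-p is not named and does not keep the true alpha at or below 0.05. ORR is secondary, but Protocol 9.3 names it as one of the two endpoints that drive the size. The smooth rise in the formula is not a property of any rule based on counts.

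**Conclusion.** The concern holds. With 20 patients, the plan states a pairing of power and alpha that the design does not have. The attainable choices are:

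- **Near the stated power:** about 24% (DCR) and 21% (ORR) chance of missing the target effect, with false-positive rates of 5.7% and 7.6%.
- **Holding 0.05:** 39.9% and 41.1% chance of missing it, with false-positive rates of 2.1% and 1.6%.

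The DCR discrepancy is small if the z-test cut-off is accepted; the ORR one is material either way. At n = 25, inside the planned range, the figures are sound and close to those stated.

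The exact results rest only on the plan's own rates, n and alpha, with independent patients and one fixed cut-off. The source of the stated figures is inferred. This should be fixed because the justification is wrong as written, but it affects how Part 2 is justified and read, not a planned test or decision. The tension between SAP 4.1 and SAP 4.3 is a separate wording matter and does not carry the finding.

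**What to change.** Change wording in Protocol 9.3 and SAP 4.3, and one line in SAP 4.1:

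1. Name the method and restate power and alpha as matched pairs, described as operating characteristics for sizing and not as decision rules. Either presentation is acceptable:
   - exact binomial holding 0.05: 60.1% (DCR) and 58.9% (ORR) at n = 20; 77.1% and 76.6% at n = 25; or
   - the approximate cut-offs with their true alpha: 76.2% at 0.057 (DCR) and 79.4% at 0.076 (ORR) at n = 20; 77.1% and 76.6%, both at 0.034, at n = 25.
2. Replace the sentence on slightly higher power with the n = 20 and n = 25 figures and a note that power does not rise steadily with n.
3. In SAP 4.1, say that no formal test is planned and that 40% and 5% are reference values for sizing.

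Optionally, report DCR and ORR with two-sided 90% Clopper-Pearson intervals, which correspond to one-sided 0.05; this would add an interval to the descriptive output.

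Items 1 to 3 cost a few sentences and change no patient numbers, data collection or planned analyses. The price is candour: the n = 20 figures will show either lower power or a higher alpha than now stated.
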